- 3) Overdose Risk Assessment: This assessment is used to determine the potential for future overdose based on prior overdose history, current drug use practices and social context for current drug use. This assessment is not standardized but is compiled from individual items of known risk factors for overdose.
- 4) World Health Organization Alcohol, Smoking and Substance Involvement Screening Test (WHO-ASSIST v.3). This is a multi-item tool to determine areas of substance use and misuse. This assessment battery screens for recent and lifetime use of a variety of substances, including illicit drugs, alcohol, pharmaceuticals and tobacco products.
- 5) EQ-5D-3L: This validated quality of life measure asks about problems in mobility, self-care, usual activities, pain and discomfort, anxiety and depression and overall health.

Locator information:

Subjects will be asked to provide a number of sources to ensure they can be contacted for follow-up visits. However, because we anticipate a number of subjects to have unstable housing, subjects may be enrolled if they provide at least one primary source of locator information.

Randomization

Subjects will be randomized to receive either standard of care or the study intervention. We will recruit equal numbers of subjects in the intervention and control arms of the study.

Follow-up Visits

Follow-up visits will occur at 1 and 6 months after enrollment. Interviews will be by phone or in-person. Assessments given at the baseline interview will be repeated at each follow-up point. In

addition to the assessments subjects will be asked questions in the intervention arm about how well the treatment navigation process is working.

Secondary Data Sources

Secondary data on health care and drug treatment utilization will be obtained from Washington State (separate IRB action pending) using the following sources:

- Division of Behavioral Health and Recovery (DBHR) data for drug treatment admissions data (formerly TARGET) and King County Behavioral Health and Recovery Division
- The Comprehensive Hospital Abstract Reporting System (CHARS) for hospital admissions
- Criminal History data extracted from Administrative Office of the Courts (AOC) and Department of Corrections (DOC) by the Washington Institute for Public Policy (WSIPP)
- Emergency Department Information Exchange data for emergency department visits administered by Collective Medical Technologies.

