The Data Safety Monitoring Oversight Committee will have 2-4 representatives who have clinical and research expertise relevant to the study. They are not directly involved in study procedures. They will meet during the period of study planning, one month and 4 months after the study is initiated. The committee will receive reports on the progress of the study prior to the meeting, including the number and characteristics of subjects and those who declined to participate. Any serious adverse events (SAE) will be discussed with the committee to determine if the risks of SAE could be modified by any changes in study procedures. Other reports will be provided as the committee requests. Committee membership will be determined prior to study initiation.

Drug accountability

Study medication will be ordered and prescribed by Kelly-Ross Pharmacy in Seattle. Upon receipt, the investigator is responsible for taking inventory of the investigational agent. A record of this inventory will be kept and usage will be documented. Any unused or expired investigational agent shall be accounted for.

Adverse event reporting

The risks expected from trials employing behavioral interventions are presumed minimal and the medication being prescribed for possible future use is designed to be used to prevent a fatal overdose with side effects being rare. However, given the nature of ongoing drug and/or medication use the population studied in this trial is possibly at risk for an overdose. Adverse events (AEs) will be categorized as serious or non-serious, as related or not related to the study, and as expected or unexpected. An AE is defined as any reaction, side effect, or untoward event that occurs during the course of the clinical trial. Stable chronic conditions, such as substance abuse, which are present prior to clinical trial entry and do not worsen, are not considered AEs. Common, minor ailments and complaints will be excluded from any type of documentation. These may include: colds, flu's, cuts, scrapes, coughs, headaches, stomach complaints, and general fatigue.

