Serious adverse events (SAEs) are defined as any fatal event, any immediately life threatening event, any permanent or substantially disabling event, any event that requires or prolongs inpatient hospitalization, congenital anomaly or birth defect, or any event requiring intervention to prevent any of the previously listed serious events. Hospital visits that do not result in admittance are not considered SAE's (e.g. emergency room visit for a non- study-related injury that does not result in admittance). Normal childbirth and pre-planned elective procedures are not considered SAEs. AE/SAE's will be elicited by interventionists/research interviewers at each assessment visit by asking the participants if they have noticed any new problems or existing problems that have gotten worse (using the Adverse Events Worksheet).

Disclosure of an AE/SAE may also occur in an unsolicited manner to a research or clinical staff member. The interviewers should be focused on gathering data to aid in determining study relatedness. Study-relatedness will be determined by the interviewers in consultation with one of

the investigators. All AEs and SAEs will be recorded in the AE/SAE log and entered into the secured project database. AEs that are not study related do not require any further paperwork documentation besides the AE Log. In this study, potential AEs that may be related to the study would be an increase in emotional distress in relation to discussion of past or current drug use behaviors *or side effects of naloxone*.

University of Washington Adverse Events reporting requirements

The term adverse event is generally used to refer to any untoward or unfavorable medical occurrence in a human subject, including any abnormal sign (for example, abnormal physical exam or laboratory finding), symptom, or disease, temporally associated with the subject's participation in the research, whether or not considered related to the subject's participation in the research. Adverse events encompass both physical and psychological harms. They occur most commonly in the context of biomedical research although, on occasion, they can occur in the context of social and behavioral research.

Unanticipated problems, in general, include any incident, experience, or outcome that meets all of the following criteria:

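### Hospital admissions are SAEs found by self-report and also an outcome with a records source, and no step compares the two, so admission-type SAEs may be under-recorded

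*Combined protocol and SAP*

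**What the plan says.** **Definition.** The Adverse event reporting section lists among serious events "any event that requires or prolongs inpatient hospitalization", whether or not the study caused it. It then carves out two kinds of admission: "Normal childbirth and pre-planned elective procedures are not considered SAEs". Hospital visits that do not lead to admittance are also outside the definition. All AEs and SAEs are to go into the log and the project database.

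**How SAEs are found.** The same section says that AEs and SAEs "will be elicited by interventionists/research interviewers at each assessment visit by asking the participants" about new or worsening problems. It adds a passive route: "Disclosure of an AE/SAE may also occur in an unsolicited manner to a research or clinical staff member". The Follow-up Visits section sets the schedule: "Follow-up visits will occur at 1 and 6 months after enrollment".

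**How admissions are found.** Hospitalization is among the Aim 4 outcomes in the Abstract and the Data Analysis Plan. The Secondary Data Sources section lists "The Comprehensive Hospital Abstract Reporting System (CHARS) for hospital admissions", with a separate IRB action still pending. The Data Analysis Plan names no source for the hospitalization outcome, but CHARS is the only one listed for admissions.

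**Who uses the SAEs.** The Data Safety Monitoring Oversight Committee section says: "Any serious adverse events (SAE) will be discussed with the committee to determine if the risks of SAE could be modified" by changing study procedures. The committee's listed meetings are during planning and at 1 and 4 months after initiation.

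**The concern.** One admission can serve two purposes in this trial, and each purpose has its own source. As a safety event it depends on the subject remembering it, regarding it as a new or worse problem, and being reached to say so. As an outcome it can come from a hospital record that needs no interview. Nothing brings the two together, so a qualifying admission could count toward the hospitalization result and never reach the log or the committee.

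Several features make missed reports plausible. Five months separate the two follow-up visits. The Locator information subsection expects unstable housing and accepts a single contact source. The Secondary Data Sources section rules out contact while a subject is incarcerated, so a subject in jail at month 6 is not asked then.

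Capture could also differ by arm. Intervention subjects meet the Treatment Navigator through the 6 months and so have more occasions to volunteer an event; no equivalent contact is described for controls.

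At stake is the completeness of the safety record, and whether the pilot ends with two accounts of admissions that it cannot explain.

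**Working it through.** **1. Is there a link anywhere?** The plan states no expected SAE count, admission rate or retention rate, so there is no figure to reproduce. The check is a reading of every section that could connect the records with the log.

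- Secondary Data Sources: lists CHARS and does not mention the log. A records request tied to an event is described only for cause of death.
- Adverse event reporting: gives the two routes above and does not mention hospital records.
- Data Safety Monitoring Oversight Committee: the committee receives progress reports and discusses SAEs. It may ask for other reports, but none on recorded admissions is specified.
- Study monitoring: submitted data are checked against source documents, and safety monitoring is an area of particular concern. Neither CHARS nor the log is named.
- Data monitoring: health services data are made into analytic sets, with no onward step to safety.

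No link is described.

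**2. How much could be missed? (illustration)** N = 100 comes from the Abstract. The rest is assumed, because the documents give no rates: r = share of subjects with a qualifying admission (at most one each), v = share interviewed, s = share of admissions reported by those interviewed.

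Missed = N × r × (1 − v × s). P(at least one missed) = 1 − [1 − r(1 − v × s)]^N.

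- r = 0.10, v = 0.90, s = 1.00: missed = 100 × 0.10 × 0.10 = 1 of 10; P = 1 − 0.99^100 = 0.63.
- v = s = 0.90: v × s = 0.81, so 19% are missed.
- v = 0.80, s = 0.75: v × s = 0.60, so 40% are missed: 4 of 10 at r = 0.10, 8 of 20 at r = 0.20.
- r = 0.30, v = s = 0.60: missed = 100 × 0.30 × 0.64 = 19.2 of 30; P > 0.99.
- v = s = 1: none missed.

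The formula credits nothing to the month-1 visit or to volunteered reports among subjects who miss month 6. It therefore overstates the loss for given v and s.

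**3. Which count would be larger?** Take 20 true admission-type SAEs (assumed).

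- Records capture 70% and self-report 90%: records 0.70 × 20 = 14, log 0.90 × 20 = 18. The log is larger.
- Records complete, with 10% of recorded admissions of excluded types: records 20/0.90 = 22.2, log 18. Of the gap of 4.2, 2.2 is definitional and 2 is under-recording.
- The same with 20% excluded: records 20/0.80 = 25, log 18. Of the gap of 7, 5 is definitional and 2 is under-recording.

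A raw difference between the counts therefore does not measure under-recording. Subject-level matching is needed.

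**4. Could the committee see the matched data at a listed meeting?** The first subject completes 6 months no earlier than month 6 after initiation. The last listed meeting is at month 4. A full match cannot reach any listed meeting.

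**The case against.** The strongest reply is that this is an optional refinement in a 100-subject feasibility pilot. Record access awaits a separate IRB decision, and completeness is not stated, so CHARS cannot be treated as the truth. Scheduled questioning does not differ by arm. The Adverse Events Worksheet is not reproduced and may prompt for hospital stays. The committee can request further reports, and monitoring already covers agreement with source documents. All of this stands as a limit on the claim, but none of it supplies the missing comparison.

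Four stronger readings are tempting, and the documents do not support them:

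- *The SAE count will fall below the admission count.* This depends on unstated retention, reporting and record coverage. The two totals are also not meant to agree: some admissions are not SAEs, and deaths or other serious events without an admission are.
- *Some fixed share, such as 19% or 40%, will be missed.* These figures rest wholly on assumed inputs and ignore two reporting opportunities.
- *The intervention arm will look less safe.* Navigator contact gives more chances to disclose, but nothing shows how many more events would surface, and the Data Analysis Plan sets out no comparison of SAEs between arms.
- *The full trial will inherit a wrong safety figure.* The Data Analysis Plan carries effect sizes forward for sample-size planning; it does not mention SAE totals.

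It is also true that the university's adverse event form applies only where study causation is more likely than not. Unrelated admissions absent from the log would not change those submissions. The plan nevertheless requires every SAE to be logged, related or not.

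**Conclusion.** The point holds as a gap in ascertainment. Qualifying admissions are SAEs by the plan's own definition, the described routes to the log are self-report and volunteered disclosure, admission records are planned for other purposes, and nothing reconciles the two. Admission-type SAEs may be under-recorded, possibly unequally by arm.

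The documents give neither the size nor the direction. The range of 1 to about 19 missed subjects follows from assuming 10–30% admitted, 60–90% interviewed and 60–100% of admissions reported, and it errs high for the reason given in the working. The conclusion needs only that at least one qualifying admission goes unreported and appears in CHARS. That is plausible in this population but not certain.

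This is a minor, inexpensive improvement. It does not threaten the pilot's feasibility aims.

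**What to change.** Add the following to the Adverse event reporting section:

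- Once the record data are approved and received, match CHARS admissions in the 6 months after each subject's enrollment to the AE/SAE log, by subject and in both arms.
- Enter each unlogged admission that meets the section's SAE definition as a record-identified SAE, keeping the existing exclusions. Assess relatedness where the record allows; otherwise mark it not assessable.
- Send these events to the oversight committee in a supplementary report, since its listed meetings come too early.
- Report admission-type SAE counts by arm before and after matching, and identify the admissions excluded by definition.

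Emergency-department visits without admittance are not SAEs under the plan and need not be entered.

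**Cost.** One merge of data that the trial already intends to obtain, a relatedness review (4 to 8 events if 40% of 10 to 20 admissions were missed, an assumption), and one extra committee report. The reported SAE count may rise, some events will be entered late, and records may say little about relatedness. The step depends on the pending IRB action. It improves the final safety record and does not protect subjects in real time.

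### The no-admittance exclusion leaves the serious label of an overdose discharged from the emergency room unclear, and no death-record check is described for subjects who cannot be located

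*Combined protocol and SAP*

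**What the plan says.** All references are to the combined protocol and SAP.

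**Seriousness.** Adverse event reporting lists the SAE criteria. Besides death and inpatient hospitalization they include "any immediately life threatening event, any permanent or substantially disabling event" and "any event requiring intervention to prevent any of the previously listed serious events". Neither of these depends on admission. The next sentence states that "Hospital visits that do not result in admittance are not considered" SAEs. Its one example, introduced by e.g., is an emergency room visit for an injury unrelated to the study. The same section says that "the population studied in this trial is possibly at risk for an overdose" and that "Adverse events (AEs) will be categorized as serious or non-serious".

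**Ascertainment.** AEs and SAEs "will be elicited by interventionists/research interviewers at each assessment visit by asking the participants if they have noticed any new problems" or a worsening of existing ones. The section adds that "Disclosure of an AE/SAE may also occur in an unsolicited manner". Follow-up Visits schedules interviews at months 1 and 6.

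**Deaths and unlocated subjects.** Secondary Data Sources provides for asking the county Medical Examiner or state Vital Records for the cause when a subject dies. For a subject who cannot be found, it names the county jail look-up and nothing further.

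**The concern.** An overdose reversed in the emergency room and discharged is a foreseeable event here: the protocol recognizes overdose risk, and Study Medication has the training urge subjects to call 911. Staff must label each event serious or not, and for this one the text supports both answers. The label has consequences. The Data Safety Monitoring Oversight Committee section commits to discussing SAEs with a view to changing procedures. An event judged unrelated needs no paperwork beyond the log.

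For deaths, the difficulty is that a subject who has died cannot be asked about problems at a visit. The Introduction identifies the period just after release as one of high fatal-overdose risk. Locator information expects unstable housing and accepts a single contact source. Subjects who cannot be found are therefore to be expected, and some of them may have died. If those deaths go unnoticed, the fatal-SAE count and the reasons for non-retention are wrong in a pilot meant to inform a full trial.

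**Working it through.** The plan gives no figure to reproduce on this point, so most of the check is a comparison of text.

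**1. The seriousness rule.** Take an immediately life-threatening overdose that is treated in the emergency room and discharged.
- Under the definition it is serious, through the life-threatening criterion and possibly the preventive-intervention criterion.
- Under the exclusion, read literally, it is not serious, because the visit ended without admission.
- The example does not settle the matter. It illustrates the exclusion without limiting it, and it concerns an unrelated injury.
- No other section states which sentence prevails.

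**2. Routes by which a death could become known.**
- Interview at a visit: not possible for a subject who has died.
- Unsolicited disclosure: possible, but not systematic.
- Medical Examiner or Vital Records: used once a death is known, to obtain its cause.
- Jail look-up: its stated use is to find subjects who may be in custody. No step is given if it finds nothing.
- Other secondary data (treatment admissions, hospital admissions, criminal history, emergency department visits): none is a death-record source, and none is assigned to vital status or SAE ascertainment.

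**3. Interval between scheduled interviews.** From Follow-up Visits: 6 − 1 = 5 months. Study Medication refers to three follow-up interviews, but only these two times are given, so the 5 months rests on the Follow-up Visits section.

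**4. Effect on the counts.** Let n subjects be enrolled, with r retained, L recorded as lost and D recorded as dead, and take these as the only categories, so n = r + L + D.
- If one death goes unnoticed, the record shows L + 1 and D − 1.
- The retained proportion r/n does not change.
- The Abstract plans 100 subjects, half per arm. One mislabelled subject is 1/100 = 1% of the trial and 1/50 = 2% of an arm.

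**5. Difference between arms.** Intervention Description gives the intervention arm navigator meetings throughout the 6 months, and the control arm has no counterpart. An unnoticed death may therefore be more likely in the control arm. This is an inference about contact, and no rate is available to size it.

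**The case against.** On seriousness, the exclusion is naturally read as clarifying the hospitalization criterion. It speaks of visits, whereas the definition speaks of events; its example is an unrelated injury; and the following sentence, on childbirth and elective procedures, looks like the same kind of carve-out for routine care. Little also depends on the label. The section says "All AEs and SAEs will be recorded in the AE/SAE log", Data monitoring has the committee review any adverse events, the committee may request other reports, and the university's adverse event form turns on attribution rather than seriousness. The narrower reading is plausible and the safeguards are real. But the text does not state that reading, so the label and the SAE-specific discussion remain uncertain.

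On deaths, subjects are asked for several contact sources, must have a phone or email, and are excluded if their contact information is inadequate. A death may also come to light informally. Mortality is not a named outcome, and no between-arm comparison of deaths is specified. These points reduce how often a death would be missed and how much depends on it. They do not supply a vital-status check. The flow diagram offered as a model and the adverse events worksheet are not in the reviewed text; the diagram may already separate deaths from losses.

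**Conclusion.** Both gaps hold, and they should be fixed. Followed as written, the plan can record a death in an unlocated subject as loss to follow-up and miss a fatal SAE, in a population the protocol itself describes as at high risk of fatal overdose. This is the more important half. The wording conflict on seriousness is secondary, because the event would still be logged and fall within the committee's general review.

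The size cannot be given as a number of events, since the documents state no overdose, admission, death or loss rate, and none is assumed here. Retention as a feasibility measure is not affected; the death count, the fatal-SAE count and the reasons for non-retention are. Confidence is medium: the first half depends on a literal reading, and the second on no vital-status procedure existing in material outside the reviewed text.

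**What to change.** - **Adverse event reporting:** reconcile the two sentences by stating that the no-admittance exclusion qualifies only the hospitalization criterion, so that an event meeting any other SAE criterion remains an SAE. This costs one clause.
- **Secondary Data Sources:** state that for every subject not located at a follow-up point, in both arms alike, the Medical Examiner and Vital Records sources already named there will be queried for vital status. This costs one or two sentences and a few extra record requests.
- **Data Analysis Plan:** show deaths separately from loss to follow-up, by arm, in the flow diagram, if the model diagram does not already do so.

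Before adopting the second change, confirm that the authorizations described under Obtain Informed Consent cover these queries. Also check whether they need ethics approval of their own, since the protocol notes a separate, pending IRB action for its health care and drug treatment utilization data.

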The Affordable Care Act (ACA) has markedly increased eligibility for health insurance coverage for releasing offenders, such that a very high proportion of offenders releasing from WA DOC prisons qualify for Medicaid coverage. Since 2014, WA DOC has launched an effort to enroll as many releasing offenders as possible into Medicaid coverage effective at the time of release resulting in a substantial majority of inmates obtaining Medicaid coverage. We are fortunate that WA HCA (Medicaid) has undertaken several initiatives to promote better integration of healthcare services including integrating medical, mental health, and substance use disorder treatment that should facilitate this study and support sustainability long term (see letter of support).

The crux of this innovation initiative is building motivation and self-efficacy for and ready access to adequate coordinated care for releasing offenders with OUD to initiate and maintain MAT. Given that MAT has the best evidence base for effective treatment of OUD, facilitating access to MAT (accompanied by psychosocial treatment as appropriate) will be the major thrust of the initiative. Our intention is to make appropriate treatment (buprenorphine, methadone, and long-acting-naltrexone) available, with the particular treatment approach selected on a case-by-case basis by the patient and medical provider. We will be working with community based partners who will be providing MAT including, but not limited to [name], co-investigator and Evergreen Treatment Services (see letter of support). These partners will be responsible for all medical and related care

including counseling as indicated, we will be coordinating with them and the study participants to facilitate care.

Study Design

Eligibility Criteria

Inclusion criteria

- 1) Meets DSM-5 criteria for opioid use disorder (at least 2 criteria) or were receiving treatment for opioid use disorder in the 12 months prior to incarceration.
- 2) Released to community corrections, not currently incarcerated.
- 3) Able to understand and provide informed consent.
- 4) Has access to phone (voice or text) or email to communicate with research staff.

Exclusion criteria

- 1) Under age 18 or over age 70 at time of recruitment.
- 2) Currently enrolled in an opioid treatment program using medications.
- 3) Has not used opioids (prescription type or heroin) in the past 6 months prior to incarceration.

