- 4) Unwilling to allow access to medical or drug treatment records, criminal history or criminal activity records.
- 5) Inability to communicate in English verbally.
- 6) Inability to provide adequate contact information to assist with follow-up.
- 7) Not planning on being in King County or reporting to community corrections in King County for 6 months.
- 8) Violent or overtly hostile/threatening towards research staff.
- 9) Entering 31 days or more controlled environment in the next 6 months.

Potential Subjects Identified

Recruitment, baseline interviews, and some follow-up interviews (if convenient for the subject) will take place in community corrections offices (CCOs) throughout King County. We will concentrate initially on offices in Seattle and South King County. Department of Corrections (DOC) will run weekly reports on inmates for upcoming releases to King County CCO facilities. DOC will notify CCO staff that a potential subject will be released to that facility. Once released, we will approach, recruit and enroll them during their first visit at the community corrections office and randomize to treatment as usual or intervention.

Obtain Informed Consent

Written informed consent will be obtained from all subjects who wish to participate in the study. Subjects will also be asked to complete HIPAA authorization agreements for treatment and medical records information and other secondary data sources.

Eligibility Screening

Subjects will be men or women aged 18-70 released from Washington State prisons to community corrections supervision in King county, meeting at least mild severity for Diagnostic and Statistical Manual of Mental Disorders Fifth Edition (DSM-5) criteria for diagnosis for opioid use disorder (e.g.

opiate dependence). Subjects will be asked to complete an eligibility screening questionnaire. The items covered are general demographics, proximity to the research settings, drug use questions, and DSM 5 checklist.

Baseline Assessments

Eligible subjects will undergo baseline assessments and provide information on personal information and health:

- 1) Opioid Use and Treatment Experiences: This assessment captures opioid use, overdose history, past treatment and feelings about future treatment.
- 2) Education, Employment, Income and Housing: This assessment captures other demographic information related to subject's resources and social stability.

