The number and proportion of subjects retained at each step of the study will be documented and reported in a CONSRT diagram similar to the one in the Appendix for our current RCT. Baseline characteristics will be compared for each study arm to ensure randomization was properly implemented. Bi-variate test statistics of differences in outcomes of interest will be compared by study arm and reported for all outcomes. Study analyses will begin *prior* to study completion due to the fact that this is a pilot-feasibility trial and data will be used to determine if a full randomized trial is appropriate and what modifications to the study design are needed, this is different than procedures for a full RCT where analyses would await and complete, closed dataset. Data will be used to determine the possible treatment effect sizes which will allow sample size estimates to be calculated for a future full scale randomized controlled trial.

Equitable access to care and outcomes will be examined (Beletsky et al., 2015) by comparing the characteristics of the eligible pool of offenders with those screened, enrolled, and maintained throughout the study.

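### The arm effects that will size the next trial come from unadjusted bi-variate tests, although the baseline measures are repeated at follow-up; adjusted estimates with intervals would be a low-cost gain.

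*Combined protocol and SAP*

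**What the plan says.** The Data Analysis Plan states: "Bi-variate test statistics of differences in outcomes of interest will be compared by study arm and reported for all outcomes". It names no estimator, interval or model for the effect sizes. When arms are compared, baseline characteristics are used only to see whether randomization worked. The same section says that the effect sizes will support the sample size of a full-scale trial, and that the pilot's own size is not meant for testing impact.

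The data for an adjusted analysis are already planned. Under Follow-up Visits: "Follow-up visits will occur at 1 and 6 months after enrollment" and "Assessments given at the baseline interview will be repeated at each follow-up point". Under Baseline Assessments, the opioid form is described as follows: "This assessment captures opioid use, overdose history, past treatment and feelings about future treatment". Of the ASSIST, the plan says: "This assessment battery screens for recent and lifetime use of a variety of substances". No section says which of these gives the drug-use outcome, or at which visit.

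On custody, Secondary Data Sources rules out any contact or procedure during incarceration. Follow-up Visits sets no visit window and no deferral rule. The King County Jail look-up is planned only for subjects who cannot be found. The record sources cover treatment admissions, hospital and emergency visits and criminal history; none measures drug use.

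**The concern.** With 50 subjects per arm, any effect estimate will be imprecise, and these estimates are meant to be reused. A test statistic alone does not show that imprecision to whoever plans the next trial. Leaving out a baseline value that has already been collected gives up precision for no saving in data collection.

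The secondary point is that drug use is known only from interviews. Subjects are under community supervision and recidivism is itself an outcome, so some visits can be expected to fall in custody. If custody is related to use and differs by arm, an effect among those interviewed differs from the effect among all randomized. Analyses are planned to begin before the study ends, so a rule left unwritten could be settled with outcome data in view.

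**Working it through.** **Inputs from the documents.** 100 subjects in equal arms (50 each); visits at 1 and 6 months. No alpha, power, outcome rate, standard deviation, correlation or custody rate is given, so there is no stated calculation to reproduce. Every other input below is an assumption.

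**1. Precision, scored measure.** With baseline to follow-up correlation r, ANCOVA multiplies the standard error (SE) by √(1 − r²). The unadjusted 95% half-width is 1.96 × √(2/50) = 0.392 SD.

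| r | SE reduction, formula | SE reduction, simulated (50 per arm, 20,000 runs) | 95% half-width (SD) |
|---|---|---|---|
| 0.1 | 0.5% | 0.0% | 0.390 |
| 0.2 | 2.0% | 1.4% | 0.384 |
| 0.3 | 4.6% | 4.3% | 0.374 |
| 0.5 | 13.4% | 12.9% | 0.339 |
| 0.7 | 28.6% | 28.2% | 0.280 |

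A low r is plausible for recent drug use, because of when baseline is taken: "Once released, we will approach, recruit and enroll them during their first visit at the community corrections office". Use just before that visit is restricted by prison.

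**2. Precision, binary outcome.** Simulation at 50 per arm, outcome rate 50%, binary predictor held by 30% or 50%, standardised risk difference from a logistic model (6,000 runs). The SE falls by about 0%, 1-2%, 4% and 7-8% at correlations 0.1, 0.2, 0.3 and 0.4.

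**3. Why the interval matters.** Assume true use of 60% control and 45% intervention. SE = √(0.60×0.40/50 + 0.45×0.55/50) = √0.00975 = 0.0987, about 10 points. For 80% power and two-sided 5%, the next trial needs 173 per arm at these rates. Moving the intervention rate by one SE, to 35.1% or 54.9%, gives 63 or about 1,460 per arm.

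**4. Custody.** Among those interviewed, observed use = p(1 − cU) / [p(1 − cU) + (1 − p)(1 − cN)], where cU and cN are the shares of users and non-users in custody. Take p as in step 3 and cN = 0.05 in both arms. The true benefit is 15 points.

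| cU control / intervention | Benefit seen, none interviewed later | Benefit seen, half interviewed later |
|---|---|---|
| 0.20 / 0.10 | 12.1 | 13.7 |
| 0.30 / 0.15 | 10.2 | 13.0 |
| 0.40 / 0.20 | 7.9 | 12.1 |
| 0.10 / 0.20 | 17.9 | 16.4 |
| 0.15 / 0.30 | 19.7 | 17.1 |
| 0.20 / 0.40 | 21.7 | 17.9 |
| 0.20 / 0.20 | 15.0 | 15.0 |
| 0.30 / 0.30 | 14.9 | 15.0 |
| 0.40 / 0.40 | 14.6 | 15.0 |

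The last column halves cU and cN. Example, 0.40 / 0.20 with none interviewed later: control 0.36/(0.36 + 0.38) = 0.4865; intervention 0.36/(0.36 + 0.5225) = 0.4079; difference 0.0786. The largest shift is about 7 points, or about 3 if half are interviewed later. The SE among those interviewed, with none interviewed later, is 10.4-11.1 points.

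**The case against.** The strongest reply is that this is a feasibility pilot, randomization makes the unadjusted comparison valid, and the likely gain for recent drug use or a binary outcome is a few percent of the SE at most. This stands, and it sets the weight of the point. A 5% smaller SE would narrow the one-SE range of 63 to 1,460 per arm only to about 65 to 1,215. Reporting and carrying forward the interval is therefore worth more than the adjustment itself.

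It is also fair that ANCOVA presupposes a scored outcome, and the plan defines no scored ASSIST endpoint and no drug-use time point. Naming these has to come first.

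On custody, the plan is not silent. It promises retention counts in a flow diagram and a comparison of those enrolled with those maintained, and it excludes people about to enter a controlled environment for 31 days or more. These narrow the gap, but none says how a visit in custody enters the drug-use analysis, and the exclusion cannot cover an unforeseen re-arrest. Custody is also only one cause of a missed interview, so other causes need counting too.

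Three stronger readings are tempting. A reader might infer that the bi-variate tests are biased; they are not, and only precision is lost. A reader might infer that drug-use data from subjects in custody are lost; the ban applies during incarceration, phone interviews are allowed, and no closing window is set, so a value may be delayed rather than missing. A reader might infer a drug-use bias in a known direction; the documents give no custody rates by arm, and the shift can go either way or vanish.

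**Conclusion.** The point holds as a low-cost improvement in how the pilot's effects are estimated and reported. It is not an error that invalidates the comparison, and it is not a complaint about power. For a scored measure, the gain in SE is about 0-5% at correlations of 0.1-0.3, 13% at 0.5 and 28-29% at 0.7. For binary outcomes it is small.

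The custody rule is a secondary reporting gap. Bias arises only if custody is related to use and differs by arm. The shifts of up to 7 points require a 2:1 custody ratio among users and no interview after release. They fall to about 3 points if half are interviewed later, are at most 0.4 points with equal custody, and stay below one SE throughout. Recidivism, hospitalization and treatment admission come from records and are not affected in this way, provided that the pending data access is granted. Treatment retention could share the problem if it is taken from interviews, since the treatment records are described as admissions data.

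**What to change.** In the Data Analysis Plan:

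- Name the drug-use variable and its time point, for example the ASSIST opioid score at 6 months.
- Estimate each arm effect with a 95% confidence interval, adjusted for a prespecified baseline value: ANCOVA for a scored measure, an adjusted risk difference for a binary one.
- Choose covariates that vary in this population. Yes/no use before incarceration is essentially constant, because the exclusion criteria remove anyone who "Has not used opioids (prescription type or heroin) in the past 6 months prior to incarceration". Graded opioid use would vary, as would treatment history: one route to eligibility is that subjects "were receiving treatment for opioid use disorder in the 12 months prior to incarceration", and others qualify on DSM-5 criteria.
- Keep the unadjusted results as a secondary table, and carry the interval, not only the point estimate, into the next trial's sample size.

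For custody, state whether a visit falling there is deferred to release within a stated window or recorded as in custody. Report by arm the counts using, not using, in custody and otherwise missing, and label the drug-use effect as applying to those interviewed. Counting custody as use, and as non-use, should be sensitivity results only.

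The cost is analysis wording, modest programming and a wider custody check. The present look-up covers one county jail and only subjects who cannot be located, and the criminal-history extract does not promise custody dates.
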